## **Abstract**

Morbid obesity (Body mass index > 40 kg/m^2 or 35-39 kg/m^2 with comorbidity; 37.5 kg/m^2 for Asians) is a growing global health issue. Bariatric surgery is the only intervention that has demonstrated sustainable reduction in weight and comorbidities. Among the various bariatric procedures, laparoscopic sleeve gastrectomy (LSG) has rapidly gained popularity worldwide. Physiological alterations following LSG include reduction in gastrointestinal surface and reduced retention of food. Bioavailability of drugs may be affected but published literature in this area is sparse and studies are usually small and uncontrolled. Moreover, some reports concerning gastric banding and jejunoileal bypass are no longer practiced because of the associated risk. In general, bioavailability of orally administered drug changes with a reduction in gastrointestinal area. While Kroll et al showed slight increase in area under curve of rivaroxaban post bariatric surgery, Skottheim et al demonstrated significant but variable change in systemic exposure of atorvastatin after gastric bypass (from threefold decrease to twofold increase) that diminished but was sustained with time (21-45 months post gastric bypass).

No study has investigated the change in pharmacokinetics of simvastatin post LSG.

Simvastatin is a widely-used lipid-lowering agent with a low bioavailability of 5% due to the extensive first pass metabolism. As simvastatin undergoes hydrolysis in the stomach to the active form^12, it is postulated that bioavailability of simvastatin will decrease after LSG. A decrease in bioavailability may be associated with reduced efficacy. Authors of review articles suggested choosing an alternative agent to simvastatin post bariatric surgery. However, such recommendation is largely based on theoretical concern rather than solid evidence. A previous study attempted to model the pharmacokinetics of simvastatin post Roux-en-Y and biliopancreatic diversion with duodenal switch. The data is not applicable to LSG and the model did not take into account of the pH-dependent hydrolysis. This will be the first study aiming to investigate the change in systemic exposure of simvastatin post LSG.

## **Aims & Objectives**

The aim of the study is to investigate the effect of laparoscopic sleeve gastrectomy on the pharmacokinetics of simvastatin.

## **Study design**

Study design: prospective, open, non-randomized, controlled, single-centre study

The study will be conducted with the approval from the Institutional Ethics and Research Board.

Participants: 10 patients undergoing sleeve gastrectomy

## Study Procedure

- Patient recruitment
  - o Subject selection:
    - Inclusion criteria:
      - Planned for laparoscopic sleeve gastrectomy at National University Hospital
      - Taking simvastatin
      - Aged 21 or above
    - Exclusion criteria:
      - Patient on concomitant treatment with medications/ food/ herbal supplements that may affect the pharmacokinetics of simvastatin: boceprevir, conivaptan, cyclosporine, efavirenz, mitotane, tocilizumab, rifamycin, amiodarone, amlodipine, aprepitant, azithromycin, colchicine, fenofibrate, imatinib, raltegravir, ranolazine, teriflunomide, ticagrelor, fusidic acid, protease inhibitors, telaprevir, telithromycin, gemfibrozil, erythromycin, clarithromycin, carbamazepine, rifampicin, ketoconazole, fluconazole, itraconazole, voriconazole, diltiazem, verapamil, dexamethasone, prednisolone, phenytoin, ritonavir, indinavir, nelfinavir, bosentan, telithromycin, nefazodone, St John's wort, orlistat, sibutramine and other strong CYP 3A4 inhibitors/ inducers
      - Pregnant ladies
  - o All patients referred to the National University Hospital for laparoscopic sleeve gastrectomy will be screened for inclusion into the study. Potential subjects will be screened and assessed at the Bariatric Surgery Clinic. Written consent will be taken at the Clinic. ( See Patient consent form) The potential subject's permission to be referred into a study will be obtained by the attending healthcare professionals prior to direct contact by any member of the research team, and the subject's agreement will be documented. The study aims to recruit 10 patients.
  - o Patients will be asked to stop taking simvastatin 5 days before the day of the study. Fasting is not required. Patients will also be informed that they will obtain SGD \$100 after completing the study as a token of appreciation and to compensate their time and inconvenience (if the study subject fails to complete the study, compensation will be pro-rated and paid out as \$50 per each blood sampling session).
  - Training
    - o Study members, namely [name], [name], [name], will be trained for the following: 1) Explaining procedure of the study to recruited study subjects after informed consent is taken; 2) Delivering blood sample from the bariatric clinic to the lab for storage and 3) Procedures for compensating the patient after the study
    - o Nurses of the bariatric clinic will be trained to administer the study according to the study protocol: 1) Making sure study subject is suitable for blood sampling e.g. has stopped simvastatin for 5 days, vitals stable, IV plug properly set by physician; 2) Monitoring self-administration of simvastatin by the patient; 3) Drawing blood according to the pre-set time points; 4) Monitoring patient for vitals and comfort after blood draw; 5) Documentation of details of blood sampling on the "Record for Blood Sampling"
    - o The training details (i.e. date, name of trainee and trainer, contents of training) will be recorded. Training records will be kept for 3 years after completion of the study.
  - Pre-bariatric surgery

- Recruited subjects will come to the clinic at 8:30am on the day of study. Blood taking will start at 9:30am. Fasting is not required.
- Nurses at the Bariatric Surgery Clinic will set an IV plug for blood sampling. They will also confirm with the subjects that simvastatin has been stopped for 5 days. Nurses will also check that patient has not been taking the interacting drugs in the past 5 days. The subject will take simvastatin 20mg at 9:30am (0 h). 5 mL of blood will be sampled at 0 h, 1 h, 2 h, 3 h, 5 h, 7 h. Blood sample will be taken in EDTA tubes and kept in ice. (See Record of blood sampling). Study subjects will be staying at the Bariatric Surgery Clinic and monitored by nurses who are trained for care and monitoring of patients with IV cannulation.
- All the blood samples will be transferred to the lab in ice after the last blood sample is drawn at 7 h. Blood samples will be spun down and frozen.
- Surgical procedure
  - Laparoscopic sleeve gastrectomy (LSG) is performed for most patients requiring bariatric surgery at the National University Hospital. This is a restrictive procedure where the stomach is tubularized and the excess part is removed. About 75% of the stomach will be removed in this way.
- Post-bariatric surgery
  - Patients will be invited to return to the clinic for another blood sampling session after 3 months. If the patient takes proton pump inhibitor prior to the study, the same dose should be maintained at 3 months when the patient returns for the study.
  - The blood sampling procedure for pre-bariatric surgery will be repeated.
  - \$100 will be given to patient upon completion of the second blood sampling session.

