#### Statistical Analysis

- Pharmacokinetic parameters (Area under curve, half life, Tmax and Cmax) of simvastatin and simvastatin acid before and after bariatric surgery will be calculated for each subject using pharmacokinetics software. (See Pharmacokinetics Evaluation Form) Each patient will serve as their own control and pharmacokinetic parameters before and after LSG will be compared with appropriate statistical tests (student t-test if parametric, mann-whitney u test if non-parametric).

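### With no draw between 0 and 1 h, a simvastatin peak that moves before 1 h after surgery could not be seen, and the paired AUC ratio would be biased towards the postulated decrease

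*Combined protocol and SAP*

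**What the plan says.** Under Study Procedure, in the pre-surgery session, "5 mL of blood will be sampled at 0 h, 1 h, 2 h, 3 h, 5 h, 7 h". For the visit three months after surgery, "The blood sampling procedure for pre-bariatric surgery will be repeated". Neither session has a draw between dosing and 1 h, and no reason is given for the chosen times.

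The Statistical Analysis section plans to calculate "Pharmacokinetic parameters (Area under curve, half life, Tmax and Cmax) of simvastatin and simvastatin acid before and after bariatric surgery". On the comparison it says: "Each patient will serve as their own control and pharmacokinetic parameters before and after LSG will be compared". It does not say whether AUC stops at 7 h or is extrapolated, or which AUC method is used.

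The Abstract gives the physiological premise, "Physiological alterations following LSG include reduction in gastrointestinal surface and reduced retention of food", and the expected direction, "it is postulated that bioavailability of simvastatin will decrease after LSG". It gives no Tmax, gastric emptying time or absorption rate for simvastatin or its acid.

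**The concern.** A paired design removes sampling error only if the error is alike at both sessions. The draw times are the same, but the curve may not be. If the operation shortens gastric retention of the dose, absorption may shift into the first hour, where nothing is sampled. The straight line from 0 to 1 h then cuts off more area after surgery than before, and the paired AUC ratio falls for a reason unrelated to bioavailability. That is the direction the study postulates. The floor of 1 h on Tmax would also shrink or hide a real change in peak time, which is one of the planned comparisons.

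The error is systematic, so more patients would not reduce it, and it cannot be repaired once the samples have been taken.

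**Working it through.** The plan has no figure to reproduce, so the check compares true curves with what the planned times would record.

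**Inputs from the documents:** draws at 0, 1, 2, 3, 5 and 7 h at both sessions; AUC, Cmax and Tmax compared within patient.

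**Assumptions (not in the documents):** one-compartment oral model with clearance, volume and total exposure equal at both sessions, so that only the absorption rate ka changes. ka is 0.7, 1.0 or 1.5/h before and 3, 4 or 6/h after; half-life is 1.5, 2, 3 or 4 h. That makes 3 × 3 × 4 = 36 scenarios without noise.

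**Formulas**
- ke = ln 2 / half-life
- C(t) = [ka·ke / (ka − ke)] · (e^(−ke·t) − e^(−ka·t)), scaled so that total AUC = 1
- peak time = ln(ka/ke) / (ka − ke)
- recorded AUC0-7 = linear trapezoid over the draw times
- bias = (recorded post/pre ratio) / (true post/pre ratio) − 1

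**One scenario in full:** half-life 1.5 h (ke = 0.462/h), ka 0.7 before and 4 after.

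| | Before | After |
|---|---|---|
| True peak time | 1.75 h | 0.61 h |
| C at 1, 2, 3, 5, 7 h | 0.181, 0.204, 0.173, 0.094, 0.043 | 0.320, 0.207, 0.131, 0.052, 0.021 |
| True area, 0-1 h | 0.111 | 0.290 |
| Trapezoid, 0-1 h (C at 1 h ÷ 2) | 0.091 | 0.160 |
| Area lost, 0-1 h | 0.020 | 0.130 |
| Recorded AUC0-7 | 0.877 | 0.847 |
| True AUC0-7 | 0.899 | 0.955 |

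- Recorded AUC0-7 ratio: 0.847/0.877 = 0.97. True: 0.955/0.899 = 1.06. Bias about −9%.
- Extrapolated to infinity (log-linear slope through 3, 5 and 7 h): 0.891/1.002 = 0.89, where the true ratio is 1.00.
- Recorded Cmax ratio: 0.320/0.204, about 1.56. True: 1.69.
- Recorded post-surgery Tmax: 1 h.

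**All 36 scenarios**

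| Quantity | Planned times | With a 0.5 h draw |
|---|---|---|
| Bias of AUC0-7 ratio | −2% to −12%, median −6% | 0 to −3% |
| Recorded AUC0-7 ratio, median (range) | 0.99 (0.91-1.09) | 1.04 (0.99-1.13) |
| Median ratio of AUC to infinity (true 1.00) | 0.92 | 0.97 |
| Bias of Cmax ratio | −15% to +4% (downward in 26 of 36) | −3% to +6% |
| Recorded post-surgery Tmax | 1 h in 36 of 36 | 0.5 h in 18, 1 h in 18 |

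True post-surgery peaks ran from 0.46 to 1.01 h.

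**Wider check** (half-life 1-5 h, broader absorption rates, results expressed as recorded ratio divided by true ratio):
- Parent peak at or after 1 h before surgery and before 1 h after it: AUC0-7 0.75-1.00, median 0.93, never above 1. Cmax 0.60-1.06, below 1 in about 85%.
- Both parent peaks at or after 1 h: AUC0-7 bias at most about 3%.
- Both parent peaks before 1 h: AUC0-7 0.78-1.00.
- Simvastatin acid, modelled as a metabolite peaking at 1.9 h or later: AUC0-7 0.99-1.01.

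**The case against.** **The premise is not established.** The Abstract speaks of retention of food, not of the drug, and the same sentence lists a smaller gastrointestinal surface, which the model leaves out. A reader might infer that the plan predicts a peak before 1 h and that the bias is certain. The documents do not support that. This stands: the point is conditional, and its size comes from an assumed 2- to 8.6-fold rise in ka (3/1.5 to 6/0.7).

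**A true increase is not being turned into a decrease.** The worked scenario, with 1.06 recorded as 0.97, invites that reading. But total exposure is equal by construction, and 1.06 arises only because the area stops at 7 h. Read as a measure of total exposure, the recorded AUC0-7 has a median of 0.99 on the planned times and 1.04 with the added draw, so the fix brings that quantity no closer to 1.00. This also stands. It does not dispose of the point, because on the planned times the truncation and the lost early area merely happen to offset each other. AUC extrapolated to infinity lacks that offset, and there the planned times do worse (0.92 against 0.97). The plan does not say which AUC it will use.

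**The loss is not confined to one session.** Pre-surgery area and peaks are missed too (0.020 against 0.130 of area in the scenario above), which is why Cmax bias is sometimes upward. The supportable word is mainly.

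**Cmax shows no false decrease.** The recorded Cmax ratio exceeded 1 in all 36 scenarios (1.13-1.56), so faster absorption would still leave a trace. This stands.

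**Acid and noise.** The Abstract treats the acid as the active form, and it is barely affected if it peaks later. Nor has it been shown that about 6% would change a conclusion in 10 patients whose food intake is not standardised. Both stand, and both limit the weight of the point.

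**Conclusion.** The point holds as a conditional one about parent simvastatin. It is certain that a peak before 1 h cannot be seen and that recorded Tmax has a floor of 1 h at both sessions. If surgery moves the parent peak from at or after 1 h to before it, the paired AUC ratio is biased towards the postulated decrease: by about 2% to 12% for AUC0-7 under the stated assumptions, and to a median of about 0.92 for extrapolated AUC when exposure is truly unchanged. The bias is negligible to small if both peaks are at or after 1 h, and negligible for a later-peaking acid. All sizes rest on assumed absorption rates and half-lives, because the documents supply none. The case for change rests on its low cost and on the fact that the loss cannot be recovered later. It does not show that the study's result would be wrong.

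**What to change.** Add one draw at 0.5 h at both sessions, through the IV plug already in place, so that the times are 0, 0.5, 1, 2, 3, 5 and 7 h. In the 36 scenarios this cuts the AUC0-7 ratio bias to between 0 and -3% and allows a Tmax before 1 h to be recorded. It does not remove all error: peak time is still read from a coarse set of times, and Cmax bias of a few percent either way remains.

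The cost is one more tube of 5 mL or less per session, 1 × 2 × 10 = 20 more samples in the single LC-MS run, and a minor amendment to the sampling record and the blood volume in the consent form. No extra visit, staff or cannulation is needed. If the total must stay at 6 × 5 = 30 mL per session, seven tubes of about 4.3 mL (30/7) achieve that.

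### Does holding every EDTA tube on ice until after the 7 h draw undermine the before/after comparison of simvastatin acid?

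*Combined protocol and SAP*

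**What the plan says.** All of this is in the combined protocol and SAP.

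- **Sampling (Study Procedure, Pre-bariatric surgery):** "5 mL of blood will be sampled at 0 h, 1 h, 2 h, 3 h, 5 h, 7 h". On tubes and holding: "Blood sample will be taken in EDTA tubes and kept in ice".
- **Transfer and processing (same section):** "All the blood samples will be transferred to the lab in ice after the last blood sample is drawn at 7 h". The next sentence reads "Blood samples will be spun down and frozen". There is no maximum time from draw to spin, no stabiliser and no stability figure.
- **Training:** study members are trained in "Delivering blood sample from the bariatric clinic to the lab for storage". Clinic nurses are trained in "Documentation of details of blood sampling on the" blood sampling record, a form that is cited but is not in the text available.
- **Second session (Post-bariatric surgery):** the same sampling procedure is repeated at 3 months.
- **Analysis (Statistical Analysis):** AUC, half-life, Tmax and Cmax of simvastatin (lactone) and of simvastatin acid are compared before and after surgery, each patient being their own control. The named tests are a t-test or a Mann-Whitney test. No ratio and no log transformation is specified.

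**The concern.** Lactone and acid are separate analytes, and the acid is the hydrolysis product of the lactone. Any hydrolysis in the waiting tube would move drug from one analyte to the other before the assay, and the two could not be separated afterwards. The wait is uneven: the early tubes, where lactone is highest, wait longest, and the 7 h tube has no wait before transfer. Half-life and Cmax could therefore be distorted as well as AUC.

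Identical handling at both sessions does not guarantee cancellation. On the ratio scale the error in acid cancels only if surgery changes lactone and acid by the same factor, with the same profile shapes and the same delays. The plan's own rationale gives reason to expect unequal change. The Abstract says "As simvastatin undergoes hydrolysis in the stomach to the active form", and of the operation the Study Procedure says "About 75% of the stomach will be removed in this way". If acid fell more than lactone, contamination would pull the acid ratio towards the lactone ratio and understate the effect the study is looking for. The assay runs only after all 10 patients' samples are collected, so a problem would come to light too late to change handling.

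**Working it through.** The plan states no figure on this point, so there is none to reproduce.

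**1. Waiting times (from the document).** Hold = 7 − draw time. For draws at 0, 1, 2, 3, 5 and 7 h this gives 7, 6, 5, 4, 2 and 0 h, plus an unstated transfer time. The 0 h tube is drawn at dosing after 5 days off the drug and should hold little of it, so the longest wait that matters is about 6 h.

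**2. Assumptions (not in the document).**
- One-way conversion of lactone to acid at rate k = 0.1, 0.5 or 1% per hour.
- One-compartment shapes: lactone ka 1.5, ke 0.3; acid ka 0.6, ke 0.35 (per hour).
- Before surgery, lactone AUC scaled to 1 and acid AUC to 0.5. True acid ratio 0.60, so acid AUC is 0.30 after surgery.
- Linear trapezoid over the six planned times; transfer time excluded.

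**3. Formulas.** Fraction converted in a tube: f = 1 − exp(−k × hold). Measured acid = true acid + f × lactone. Let c be the trapezoid AUC of f × lactone before surgery. If lactone changes by factor r with its shape unchanged:
- measured acid AUC before = 0.5 + c
- measured acid AUC after = 0.3 + r × c

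**4. Contamination within a session.** At 1% per hour f is 6.8, 5.8, 4.9, 3.9, 2.0 and 0% across the six tubes.

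| k per hour | c | acid AUC inflation, c/0.5 | lactone AUC loss, c/1 |
|---|---|---|---|
| 0.1% | 0.0041 | 0.8% | 0.4% |
| 0.5% | 0.0201 | 4.0% | 2.0% |
| 1% | 0.0398 | 8.0% | 4.0% |

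**5. Effect on the before/after comparison (truth: ratio 0.60, difference 0.30 − 0.50 = −0.200).**

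| k per hour | ratio, r = 1 | difference, r = 1 | ratio, r = 0.60 | difference, r = 0.60 |
|---|---|---|---|---|
| 0.1% | 0.6032 | −0.200 | 0.600 | −0.2016 |
| 0.5% | 0.6155 | −0.200 | 0.600 | −0.208 |
| 1% | 0.6295 | −0.200 | 0.600 | −0.216 |

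Example at 1% per hour with r = 1: (0.3 + 0.0398)/(0.5 + 0.0398) = 0.3398/0.5398 = 0.6295, and 0.3398 − 0.5398 = −0.200.

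The two scales fail in opposite situations. With lactone unchanged, the ratio moves and the difference does not. With both analytes at 0.60, the ratio is exact and the difference is overstated by 0.8, 4.0 and 8.0%. With lactone at 0.80 the ratio reads 0.6016, 0.6077 and 0.6147. The lactone ratio itself is exact at every rate if its shape is unchanged.

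**6. Sensitivity at 1% per hour, lactone unchanged.** With acid AUC a quarter of lactone AUC the ratio reads 0.655; with the two equal it reads 0.615. Changing the lactone shape after surgery gives 0.624 to 0.636.

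**7. Comparison with sampling error (assumed within-subject CV, n = 10 pairs, log scale).** Half-width = t(0.975, 9 df) × √(ln(1 + CV²)) × √(2/10).
- CV 20%: 2.262 × 0.198 × 0.447 = 0.200; interval 0.60 × exp(±0.200) = 0.49 to 0.73.
- CV 50%: 2.262 × 0.472 × 0.447 = 0.478; interval 0.60 × exp(±0.478) = 0.37 to 0.97.

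A shift of 0.03, or 0.055 in the least favourable case of step 6, is well inside even the narrower interval.

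**8. What prompt handling would buy.** Spinning each tube 30 min after its draw gives 0.6004, 0.6020 and 0.6040 at the three rates. The cost is up to 5 extra deliveries × 2 sessions × 10 patients = 100, or a centrifuge in the clinic with training in its use.

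**The case for a change.** The strongest case for a change is that the error cannot be undone, that it points towards hiding the hypothesised fall in acid, and that nothing in the text fixes equal delays at the two sessions. On the same assumed curves, with no true change, spinning the second session 1 h or 3 h later than the first gives an acid ratio of 1.018 or 1.053 at 1% per hour. A bench stability test before enrolment would be cheap. AUC is also often analysed on the log scale, where the ratio is the relevant quantity.

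Much of this stands as description. The holds are as long as stated, no time limit is written down, within-session acid values would be inflated if conversion occurs, and a larger rate would matter more: at 5% per hour the base case reads 0.706. What is missing is evidence of harm. The document places hydrolysis in the stomach and calls it pH-dependent. It says nothing about conversion in iced EDTA blood, its rate or its direction, so every size above is conditional on an assumed rate, and 5% has no support in the text. Unequal delay is possible, but the plan repeats one procedure with one transfer point, and even a 3 h discrepancy gives about 5% at the highest of the three rates tabulated. Handling times may be on the blood sampling record, which cannot be checked here.

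**Conclusion.** The concern is accurate about what is written but does not call for a change. Ice, a single fixed transfer point, the same procedure at both sessions and within-patient comparison already limit the problem for the study's stated aim, which is the effect of surgery. At assumed conversion of up to 1% per hour, the acid ratio shifts by about 0.03 in the base case and by 0.015 to 0.055 as acid AUC runs from equal to lactone AUC down to a quarter of it. The untransformed difference is either unbiased (lactone unchanged) or overstated by at most 8% (both analytes at 0.60). None of this is large beside the precision that 10 patients can give.

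A per-tube processing rule would add up to 100 deliveries or new equipment for a gain that has not been shown, and the sponsor could reasonably decline it. Confirming lactone and acid stability on ice, and logging processing times, are things a bioanalytical laboratory would be expected to cover in its own validation; their absence from a short protocol is a gap that is sensibly filled there. The conclusion rests on the assumed rates, profile shapes and CVs. It would need revisiting if the laboratory found conversion on ice well above 1% per hour.
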